1.3. Schedule of Events

Table 1: Schedule of Events

Visit Number		1	2	3	4	5, 6, 7, and 8	9	USV
Type of Visit	С	С	С	С	С	SC	С	С
Month Time Point					M1	M2-M5	M6	Up to M6
Visit Day	Screeninga	D1 ^a (Baseline)	D4	D8	D29	D57, D91, D121, D151	D181/EoS	N/A
Window Allowance (Days)	-28	-	-2	-2 or +1	-7 to +2	±5	±14	N/A
Informed consent form, demographics, medical history ^b	X							
Inclusion/exclusion criteria	X	X						
Blood collection for safety laboratory samples ^c	X			X				
Full physical examination ^d	X							
Symptom-directed physical examination ^{d,e}		X		X	X		X	X
Injection site and axillary lymph node assessment (injected arm)		X						
Vital sign measurements ^e	X	X						
ECG ^f		X						
Pregnancy testing ^g	X	X						
Randomization		X						
Study vaccination (including 60-minute postdose observation period)		X ^h						
Blood collection for humoral immunogenicity ⁱ		X		X	X		X	
Blood collection for cellular immunogenicity ⁱ		X		X	X			
Optional blood collection for genomics		X						
Optional blood collection for transcriptomics		X		X	X			
Blood sample for biomarker analysis ^j			X					
Nasopharyngeal swab for virus detection ^k		X						X
eDiary activation for recording solicited ARs (7 days) ^l		X						

Protocol: mRNA-1020-P101 Amendment 1 mRNA-1020 and mRNA-1030

Visit Number		1	2	3	4	5, 6, 7, and 8	9	USV
Type of Visit	С	С	С	С	С	SC	С	С
Month Time Point					M1	M2-M5	M6	Up to M6
Visit Day	Screeninga	D1 ^a (Baseline)	D4	D8	D29	D57, D91, D121, D151	D181/EoS	N/A
Window Allowance (Days)	-28	-	-2	-2 or +1	-7 to +2	±5	±14	N/A
Review of eDiary				X				
Follow-up safety call ^m						X		
Recording of all unsolicited AEs		X		X	X			
Recording of SAEs, AESIs, MAAEs, and AEs leading to study withdrawal		X		X	X	X	X	X
Recording of concomitant medications and nonstudy vaccinations ⁿ	X	X		X	X	X	X	X
Study completion							X	

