4. STUDY DESIGN

4.1. General Design

The study will be a Phase 1/2, randomized, observer-blind, dose-ranging study to evaluate the safety, reactogenicity, and immunogenicity of mRNA-1020 (CCI) and mRNA-1030 (CCI) in healthy adults 18 to 75 years of age. Enrollment in study arms will proceed in parallel with randomization (Figure 1) of all dose levels of mRNA-1020 and mRNA-1030 (Study Arms 1 to 6), the mRNA-1010 Comparator Arm (Study Arm 7), and the Flublok Comparator Arm (Study Arm 8). The study will randomize approximately 70 healthy adult participants into each study arm with a balanced age group representation stratified approximately 1:1 into age groups of 18 to < 50 years of age and \ge 50 to \le 75 years of age.

The vaccines to be tested contain mRNAs encoding for the surface glycoproteins of the strains recommended by the WHO for 2021/22 NH cell- or recombinant-based vaccines:

- A/Wisconsin/588/2019(H1N1)pdm09
- A/Cambodia/e0826360/2020(H3N2)
- B/Washington/02/2019 (B/Victoria lineage)
- B/Phuket/3073/2013 (B/Yamagata lineage)

Study visits will consist of a Screening Visit (up to 28 days before the Day 1 visit), Vaccination Visit at Day 1, and subsequent study visits on Day 4, Day 8, Day 29 (Month 1), and Day 181/end of study (EoS; Month 6), with up to 7 months of study participation (Table 1). Unscheduled visits for potential ILI symptoms will include testing with a multiplex respiratory infection panel (Biofire or similar).

Immunizations for the study are planned during the NH spring, when influenza infection rates are typically low or declining. Approximately 560 participants will be randomized to receive a single dose of either one of the 2 next-generation candidate vaccines (mRNA-1020 or mRNA-1030) at different dose levels, a single dose of the first-generation candidate vaccine (mRNA-1010), or Flublok, a licensed enhanced seasonal influenza vaccine comparator (8 study arms total). Three different dose levels (CCI (mRNA-1020), 3 different dose levels (CCI (mRNA-1030), and a single dose level of mRNA-1010 (50 µg total mRNA) will be assessed. A description of the mass ratios for the dose levels are provided in Table 3. The target number of participants in each arm and the randomization ratio can be found in Table 4.

ModernaTX, Inc. 16 Feb 2022 mRNA-1020 and mRNA-1030

Protocol: mRNA-1020-P101 Amendment 1

Table 3:	Mass	Ratios	for	Dose	Lev	els
----------	------	--------	-----	------	-----	-----

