- 10. Any medical, psychiatric, or occupational condition, including reported history of substance abuse, that, in the opinion of the Investigator, might pose additional risk due to participation in the study or could interfere with the interpretation of study results. Asymptomatic conditions and conditions with no evidence of end organ involvement (eg, mild hypertension, dyslipidemia) are not exclusionary, provided that they are being appropriately managed and are clinically stable (ie, unlikely to result in symptomatic illness within the time course of this study). Illnesses or conditions may be exclusionary, even if otherwise stable, due to therapies used to treat them (eg, immune-modifying treatments), at the discretion of the Investigator.
- 11. Participant has received systemic immunosuppressants or immune-modifying drugs for > 14 days in total within 180 days prior to screening (for corticosteroids ≥ 10 mg/day of prednisone equivalent) or is anticipating the need for immunosuppressive treatment at any time during participation in the study.
- 12. Participant has received or plans to receive any licensed or authorized vaccine, including COVID-19 vaccines, ≤ 28 days prior to the study injection (Day 1) or plans to receive a licensed or authorized vaccine within 28 days after the study injection.
- 13. Participant has received a NH 2021-2022 seasonal influenza vaccine or any other influenza vaccine within 180 days prior to Day 1.
- 14. Participant tested positive for influenza by CDC-recommended testing methods within 180 days prior to Day 1 (CDC 2020d).

ModernaTX, Inc. 16 Feb 2022
Protocol: mRNA-1020-P101 Amendment 1 mRNA-1020 and mRNA-1030

15. Participant has received systemic immunoglobulins or blood products within 90 days prior to the Screening Visit or plans to receive during the study.

- 16. Diagnosis of malignancy within previous 10 years (excluding nonmelanoma skin cancer).
- 17. Participant has donated ≥ 450 mL of blood products within 28 days prior to the Screening Visit or plans to donate blood products during the study.
- 18. Participated in an interventional clinical study within 28 days prior to the Screening Visit based on the medical history interview or plans to do so while participating in this study.
- 19. Participant is an immediate family member or household member of study personnel, study site staff, or Sponsor personnel.

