5.3. Lifestyle Restrictions

Participants must not eat or drink anything hot or cold within 10 minutes before oral temperature is taken. Participants in the study should defer vaccination with licensed or authorized vaccines, including COVID-19 vaccines, until after completion of their Day 29 Visit, if a licensed or authorized vaccine is available and they choose to receive it.

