The IP will be administered at the study site under direct observation of medically qualified study staff, and IP administration will be appropriately recorded (date and time) in the electronic case report form (eCRF). Qualified staff will confirm that the participant has received the entire dose of the IP. If a participant does not receive the IP, the reason for the missed dose will be recorded. Data will be reconciled with site accountability records to assess compliance.

The study site staff are responsible for ensuring that participants comply with the allowed study visit windows. If a participant misses a visit, every effort should be made to contact the participant and complete a visit within the defined visit window specified in the SoE (Table 1). If a participant does not complete a visit within the time window, that visit will be classified as a missed visit and the participant will continue with subsequent scheduled study visits. All safety requirements of the missed visit will be captured and included in the subsequent visit.

Prior and Concomitant Medications 6.5.

6.5.1. **Prior Medications and Therapies**

Information about prior medications (including any prescription or over-the-counter medications, vaccines, or blood products) taken by the participant within the 28 days before providing informed consent (or as designated in the inclusion/exclusion requirements) will be recorded in the participant's eCRF.

6.5.2. **Concomitant Medications and Vaccinations**

At each study visit, study site staff must question the participant regarding any medications taken and nonstudy vaccinations received by the participant and record the following information in the eCRF:

- All nonstudy vaccinations administered within the period starting 28 days before the IP injection and through Day 181/EoS.
- Any seasonal influenza vaccine administered from September 2021 through Day 181/EoS.
- Any authorized or investigational COVID-19 vaccine at any time before the IP injection and through Day 181/EoS.
- All concomitant medications taken through 28 days after the IP injection. Antipyretics and analgesics taken prophylactically (ie, taken in the absence of any symptoms in anticipation of an injection reaction) will be recorded as such.
- Systemic steroids (≥ 10 mg/day of prednisone or equivalent), immunosuppressants, immune-modifying drugs, immunoglobulins, and/or blood products administered at any time during the study period after the IP injection.

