- Any concomitant medications relevant to or for the treatment of an SAE, adverse event of special interest (AESI; Section 8.4.6), a medically attended AE (MAAE; Section 8.4.4), or an AE leading to withdrawal from Day 1 through Day 181/EoS.
- The participant will be asked in the eDiary if they have taken any antipyretic or analgesic medication to treat or prevent fever or pain within 7 days after the study vaccination, including the day of injection. Reported antipyretic or analgesic medications should be recorded in the source document by the study site staff during the study visits after vaccination or via other participant interactions (eg, telephone calls).

If a participant takes a prohibited drug therapy, the Investigator and the contract research organization's (CRO's) medical monitor will make a joint decision about continuing or withholding the study vaccination of the participant based on the time the medication was administered, the drug's pharmacology and pharmacokinetics, and whether use of the medication will compromise the participant's safety or interpretation of the data. It is the Investigator's responsibility to ensure that details regarding the concomitant medications are adequately recorded in the eCRF.

All medication and interventions necessary for the appropriate care of the study participant should be administered and appropriately documented along with the AE for which the treatment was initiated.

6.5.3. Concomitant Medications and Vaccines that May Lead to the Elimination of a Participant from Per-Protocol Analyses

The use of the following concomitant medications and/or vaccines will not require withdrawal of the participant from the study but may determine a participant's evaluability in the Per-Protocol (PP) analysis (see Table 8 for definition of PP Set):

- Any investigational or nonregistered product (drug or vaccine) other than the study vaccine used during the study period.
- Immunosuppressants or other immune-modifying drugs administered chronically (ie, more than 14 days in total) during the study period. For corticosteroids, this will mean that ≥ 10 mg/day of prednisone or equivalent is not permitted. Inhaled, nasal, and topical steroids are allowed
- Long-acting immune-modifying drugs administered at any time during the study period (eg, infliximab).
- An authorized or licensed vaccine administered within 28 days after the study vaccination (Section 5.2).

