1 INTRODUCTION

This statistical analysis plan (SAP), which describes the planned analyses for Study mRNA-1020-P101, is based on the protocol dated 16-Feb-2022, and the electronic case report form (eCRF), dated 21-Mar-2022. SAP will be based on the latest protocol and eCRF and will be updated as necessary.

In addition to the information presented in the SAP section of the protocol (Section 9), which provides the principal features of analyses for this study, this SAP provides statistical analysis details/data derivations.

This is a Phase 1/2, randomized, observer-blind, dose-ranging study to evaluate the safety, reactogenicity, and immunogenicity of mRNA-1020 and mRNA-1030 candidate seasonal influenza vaccines in healthy adults 18 to 75 years of age.

Parexel Biostatistics and Statistical Programming team, designee of Moderna Biostatistics and Statistical Programming department, will perform the statistical analysis of the safety, reactogenicity, and immunogenicity data; Statistical Analysis System (SAS) Version 9.4 or higher will be used to generate all statistical outputs (tables, figures, listings, and datasets). The SAP will be finalized and approved prior to the clinical database lock and treatment unblinding for the study. If the methods in this SAP differ from the methods described in the protocol, the SAP will prevail.

In this document, study vaccination, injection of investigational product (IP) / investigational vaccine, and injection are used interchangeably.

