5.3 Per-Protocol (PP) Set

The PP Set consists of all participants in the FAS who comply with the injection schedule, comply with the timings of immunogenicity blood sampling to have a baseline and at least 1 post-injection assessment, do not have influenza infection at baseline through Day 29 (as documented by PCR testing), and have no major protocol deviations that impact the immune response. The PP Set will be used as the primary analysis set for analyses of immunogenicity unless otherwise specified. Participants will be analyzed according to the vaccination group to which they were randomized.

Participants compliant with the timing of immunogenicity blood sampling are required to have a baseline assessment, at least one post-injection assessment, and a Day 29 assessment that is within 21 days to 42 days after injection (-7 / +14 days of Day 29).

Participants with a dosing error will be considered as having a protocol deviation. However, the determination of whether to include/exclude participants from the PP Set due to a dosing error will be based on the dosage difference (in μ g) between the actual dose received and the randomized dose. The PP Set exclusion criteria for participants with dosing error are described in [Table 2](#). For the mRNA-1020 and the mRNA-1030 arms, acceptable dosing deviation from the randomized dose is up to **CCI** [REDACTED]. For the mRNA-1010 active comparator, participants who are randomized to the active comparator arm but received less than **CCI** [REDACTED] of the active comparator or any amount of mRNA-1020, mRNA-1030, or Flublok active comparator will be excluded from the PP Set. For the Flublok active comparator, participants who are randomized to the active comparator arm but received less than **CCI** [REDACTED] of the active comparator or any amount of mRNA-1020, mRNA-1030, or mRNA-1010 active comparator will be excluded from the PP Set.

Table 2 PP Set Exclusion Criteria for Dosing Errors

	Randomized Dose							
	mRNA-1020	mRNA-1030			mRNA-1010 (active comparator) ¹		Flublok (active comparator) ²	
Actual Dose Received	CCI							
mRNA-1020								
	CCI	Y	Y	Y	Y	Y	Y	Y
	CCI	Y	Y	Y	Y	Y	Y	Y
	CCI	Y	Y	Y	Y	Y	Y	Y
	CCI	Y	Y	Y	Y	Y	Y	Y
	CCI	Y	Y	Y	Y	Y	Y	Y
	CCI	Y	Y	Y	Y	Y	Y	Y
	CCI	Y	Y	Y	Y	Y	Y	Y
	CCI	Y	Y	Y	Y	Y	Y	Y
	CCI	Y	Y	Y	Y	Y	Y	Y
	CCI	Y	Y	Y	Y	Y	Y	Y
	CCI	Y	Y	Y	Y	Y	Y	Y
	CCI	Y	Y	Y	Y	Y	Y	Y
	CCI	Y	Y	Y	Y	Y	Y	Y
	CCI	Y	Y	Y	Y	Y	Y	Y
	CCI	Y	Y	Y	Y	Y	Y	Y
	CCI	Y	Y	Y	Y	Y	Y	Y
	CCI	Y	Y	Y	Y	Y	Y	Y
	CCI	Y	Y	Y	Y	Y	Y	Y
	CCI	Y	Y	Y	Y	Y	Y	Y

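### Day 181 titers drawn after a permitted influenza vaccine or late influenza stay in the per-protocol summaries, and no planned Day 181 result shows the arms without them

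*SAP*

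**What the plan says.** - **Infection.** SAP 5.3 admits to the PP Set participants who "do not have influenza infection at baseline through Day 29 (as documented by PCR testing", among other conditions. Nothing in that definition concerns influenza after Day 29.
- **Non-study vaccines.** Protocol 6.5.3 lists products that may cost a participant PP status. Its entry for licensed vaccines is "An authorized or licensed vaccine administered within 28 days after the study vaccination". The entries that run for the whole study are unregistered products, immune-modifying drugs, and immunoglobulins or blood products, and a licensed influenza vaccine is none of these. Protocol 5.3 allows later doses: "Participants in the study should defer vaccination with licensed or authorized vaccines, including COVID-19 vaccines, until after completion of their Day 29 Visit".
- **Sampling.** In the Schedule of Events (Protocol 1.3) the row "Blood collection for humoral immunogenicity" is marked at Days 1, 8, 29 and 181. Day 181 is the only draw after Day 29.
- **Analysis.** SAP 6.5 bases immunogenicity on the PP Set. SAP 6.5.3 tabulates GMT, GMFR, seroconversion and 2-/3-/4-fold rise at every evaluable time point, so Day 181 is included.
- **Calendar.** Protocol 4.1: "Immunizations for the study are planned during the NH spring". The SAP introduction cites "the electronic case report form (eCRF), dated 21-Mar-2022". Protocol 6.5.2 records "Any seasonal influenza vaccine administered from September 2021 through Day 181/EoS".

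**The concern.** The plan screens for influenza and licensed vaccines up to about Day 29, in spring, when it expects little influenza. The screening then stops before the autumn in which most Day 181 samples would be drawn. A dose taken after the Day 29 Visit is permitted, so the PP condition about major deviations does not catch it. The visit windows (SAP Appendix B), the non-quantifiable and missing-data rules (SAP 6.2.5, 6.2.8) and the supportive use of the FAS (SAP 6.5) do not remove or separate such samples either.

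Day 181 carries the late part of the secondary objective, and in a descriptive study the by-arm estimates are the result. A reader who takes the Day 181 GMT as persistence of the study vaccine would credit it with any boost that came from a later vaccine or infection.

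**Working it through.** The plan gives no figure for this point. Its only design calculation, the chance of seeing at least one AE in 70 participants, reproduces (1 − 0.98^70 = 75.7%; 1 − 0.96^70 = 94.3%) but has no bearing here. The documents state no uptake, attack rate, boost or enrolment dates, so those inputs below are assumptions.

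**Step 1: when Day 181 falls.** Day 181 = Day 1 + 180 days, with a visit window of ±14 days. For assumed 2022 start dates:
- 1 Mar → 28 Aug
- 21 Mar → 17 Sep
- 31 May → 27 Nov
- 20 Jun → 17 Dec

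With even enrolment over four windows (1 Mar-31 May, 1 Mar-20 Jun, 21 Mar-31 May, 21 Mar-20 Jun) and draws on the target day, the share of draws on or after 1 Sep is 0.96, 0.96, 1.00 and 1.00. On or after 1 Oct it is 0.63, 0.70, 0.81 and 0.85.

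**Step 2: share of samples drawn after a vaccine response (p).** Assume uptake is even over 1 Sep-30 Nov (91 days) and a response takes 14 days. The share of final uptake that precedes the draw is the average over draws of min(max(draw date − 14 d − 1 Sep, 0), 91)/91. For the four windows this is 0.323, 0.429, 0.412 and 0.522. Counting both end days raises each by about 0.01.
- Final uptake 20%: p = 0.20 × 0.323 to 0.20 × 0.522 = 0.065 to 0.104.
- Final uptake 40%: p = 0.129 to 0.209.

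**Step 3: effect on GMT and GMFR.** Both are means on the log scale. If a share p of an arm's samples is boosted f-fold, the result is multiplied by f^p.

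| Boost f | Uptake 20% | Uptake 40% |
|---|---|---|
| 1 (none) | 1.00 | 1.00 |
| 2 | 1.05-1.07 | 1.09-1.16 |
| 4 | 1.09-1.16 | 1.20-1.34 |

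This covers vaccination only. PCR-confirmed influenza before the draw would add to p: a further 5% of samples boosted 2-fold multiplies the result by 2^0.05 = 1.035.

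**Step 4: rates.** Seroconversion and fold-rise rates rise by between 0 and p × (1 − rate). At an assumed true rate of 50%, the upper limit is 0.065 × 0.5 = 3 points to 0.209 × 0.5 = 10 points.

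**Step 5: between-arm ratios.** If p and f are alike in two arms, f^p cancels. Chance imbalance remains. With 70 per arm and p = 20%, the SD of the difference in p is √(2 × 0.2 × 0.8/70) = 0.068. At 1.96 SD and f = 2 the ratio moves by 2^(1.96 × 0.068) = 1.10, against a level shift of 2^0.2 = 1.15. The direction of that movement is random, whereas the level shift is upward in every arm.

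**Step 6: what the planned outputs already show.**
- SAP 6.3.4 counts influenza vaccine by group from September 2021 through Day 181, which pools doses before Day 1 with later ones. Exclusion criterion 13 ("Participant has received a NH 2021-2022 seasonal influenza vaccine or any other influenza vaccine within 180 days prior to Day 1") limits the earlier doses. Looking back 180 days from 1 Mar, 21 Mar, 31 May and 20 Jun leaves 1, 21, 92 and 112 days after 1 Sep 2021, so the mixing matters mainly for late enrollees.
- SAP 6.3.2 summarizes influenza vaccine since September 2021 with the baseline data. If that means doses before Day 1, subtraction gives a rough later count.
- SAP 6.6 counts post-baseline PCR-positive influenza by group, and SAP 6.5.3 lists titers of infected PP participants.
- SAP Appendix C, Table 5 starts its Post class after injection date + 27 days, not at a blood draw.

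None of these is tied to the Day 181 draw date, and none gives a Day 181 GMT without the affected samples.

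**The case against.** The strongest reply is that the documents never promise the study vaccine's own persisting response. SAP 2.2 and 3.2 ask for immunogenicity, as GMT and GMFR, at all evaluable time points. Summarizing every sample regardless of later events is a legitimate choice, and under it the results are unbiased. This stands. A reader might infer that the Day 181 results are simply biased, and the documents do not support that, because they state neither target.

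Second, little hangs on it. No hypothesis is tested, and the Day 29 primary endpoints, the interim analysis and the Table 3 contrasts (set at Day 29) are untouched. Participants and site staff stay blinded to the final lock, so uptake should be similar across arms and ratios should on average shift less than levels. This also stands.

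Third, later exposure is partly visible through the counts and listings in SAP 6.3.4, 6.5.3 and 6.6. It would be wrong to say that readers will see nothing of it. What they lack is the link to the draw. Nor does the planned PP listing of infected participants show that the sponsor expects such cases, since a listing can be empty.

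Fourth, leaving samples out because of a post-randomization event brings its own selection. That is true, and it is why the added summary should be supportive only.

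**Conclusion.** The gap is confirmed on the text: screening stops at about Day 29, the Day 181 summaries use the same set, and no rule separates samples drawn after a later influenza vaccine or infection. Whether this is a bias depends on a Day 181 target that the SAP leaves unstated.

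The size is unknown and may be nil. No boost is plausible where the later vaccine's strains differ (Protocol 2.1 notes that strains are re-selected twice a year) or where it adds no NA response. Uptake may also be low, because the exclusion criteria select people without a recent influenza vaccine. Under the assumptions above the vaccine-related factor is 1.00 with no boost, about 1.05-1.16 for a 2-fold boost and at most about 1.34 for a 4-fold boost.

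A reader might reach for a more extreme case, with 40% of samples affected and a 4-fold boost (4^0.4 = 1.74). Under the same timing model that would need final uptake of 0.40/0.522 = 77% to 0.40/0.323 = 124%, which is implausible or impossible, so it should not be quoted as a bound. The point is a cheap improvement to a secondary time point, not a flaw in the primary analysis.

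**What to change.** In SAP 6.5.3:
- Keep the all-samples Day 181 summary as planned.
- Add a prespecified supportive Day 181 summary that sets to missing any titer drawn after a non-study influenza vaccine or PCR-confirmed influenza, and a second version that does so for vaccine only.
- Report the number of affected Day 181 samples by arm, separately for vaccine and infection, using draw dates.
- State which Day 181 target the clinical study report will interpret.

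This needs SAP wording and programming only. Vaccination records, PCR results and sample dates are already collected, and nothing changes in what participants may receive.

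There are two costs, both confined to the supportive summary:
- **Precision.** From 70 per arm, losing 10% or 20% leaves 63 or 56. Confidence intervals on the log scale widen by 1/√(1 − p), about 5% or 12%.
- **Selection.** If a share q is infected and had prior titers r-fold below the arm's GMT, dropping them raises the GMT by r^(q/(1−q)). For r = 2 and assumed q = 1%, 5% or 10% this is 1.007, 1.037 or 1.080. The vaccine-only version avoids this part, though people who seek a later vaccine may also differ from those who do not. The supportive result should be read beside the all-samples result and should not replace it.
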